6.2.12 Exposure to Study Drug

Exposure to study drug will be calculated as follows from the date of last dose (or the date of completion/termination if not present) minus the date of first dose + 1. The exposure calculation will not take into account breaks in therapy.

Duration of exposure (in days) will be calculated as follows:

- Date of Last Dose (or the Date of Completion/Termination if not present) of study drug (irrespective of dose) – Date of First Dose of study drug + 1

6.2.13 Study Drug Compliance

Study drug compliance will be calculated by comparing the amount of drug dispensed and drug returned for each participant as follows:

QMD [REDACTED]	[REDACTED]
Confidentiality Statement	
This document is the property of [REDACTED] and may not be duplicated, copied, altered or removed from company without prior approval from [REDACTED] or in compliance with [REDACTED].	

[REDACTED]

Controlled Quality Management Document	
	Sponsor: Pliant Therapeutics Inc.
	Protocol Number: PLN-74809-IPF-202
STATISTICAL ANALYSIS PLAN. PHASE 2-3-4	

Number of [REDACTED] = Total dispensed – Total returned (if the number returned is missing, a value of 0 will be used).

Expected [REDACTED] [REDACTED] = Number of days on study (calculated as per Section 6.2.12 for duration of exposure) × [REDACTED] for the relevant study part and dose group (per the table below).

Compliance (%) = (Number of [REDACTED] / Expected number of [REDACTED]) *100

Number of [REDACTED] per study part and dose group

[REDACTED]	[REDACTED]
	[REDACTED]
	[REDACTED]
	[REDACTED]
	[REDACTED]
	[REDACTED]
	[REDACTED]

6.2.14 Imperial to Metric Unit Conversion

Measurements provided in inches (in), pounds (lb) and degrees Fahrenheit (°F) will be converted to centimeters (cm), kilograms (kg) and degrees Celsius (°C) respectively, using the following conversion calculations:

- $x (cm) = x (in) \times 2.54$
- $x (kg) = x (lb) \times 0.45359237$
- $x (°C) = [x (°F) - 32] / 1.8$

Confidentiality Statement	
This document is the property of [REDACTED] and may not be duplicated, copied, altered or removed from company without prior approval from [REDACTED] or in compliance with [REDACTED].	

[REDACTED]

6.2.15 Inexact Values

In the case where a variable is recorded as “> x”, “≥ x”, “< x” or “≤ x”, a value of x will be taken for analysis purposes.

[REDACTED]

[REDACTED]

[REDACTED]

[REDACTED]

[REDACTED]	[REDACTED]
[REDACTED]	[REDACTED]
[REDACTED]	[REDACTED]
[REDACTED]	[REDACTED]

[REDACTED]

[REDACTED]

- [REDACTED]
- [REDACTED]
- [REDACTED]

[REDACTED]

		Controlled Quality Management Document	
		Sponsor:	Pliant Therapeutics Inc.
		Protocol Number:	PLN-74809-IPF-202
STATISTICAL ANALYSIS PLAN. PHASE 2-3-4			

[REDACTED]

[REDACTED]

[REDACTED]

- [REDACTED]
- [REDACTED]
- [REDACTED]
- [REDACTED]
- [REDACTED]
- [REDACTED]
- [REDACTED]
- [REDACTED]
- [REDACTED]
- [REDACTED]

[REDACTED]

[REDACTED]

[REDACTED]	[REDACTED]	[REDACTED]
[REDACTED]	[REDACTED]	[REDACTED]
[REDACTED]	[REDACTED]	[REDACTED]
[REDACTED]	[REDACTED]	[REDACTED]
[REDACTED]	[REDACTED]	[REDACTED]
[REDACTED]	[REDACTED]	[REDACTED]

[REDACTED]

- [REDACTED]
- [REDACTED]
- [REDACTED]
- [REDACTED]

[REDACTED]	[REDACTED]
Confidentiality Statement	
This document is the property of [REDACTED] and may not be duplicated, copied, altered or removed from company without prior approval from [REDACTED] or in compliance with [REDACTED].	

[REDACTED]

Controlled Quality Management Document		
	Sponsor:	Pliant Therapeutics Inc.
	Protocol Number:	PLN-74809-IPF-202
STATISTICAL ANALYSIS PLAN. PHASE 2-3-4		

[REDACTED]

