7.11 Pharmacodynamic Assessments (Biomarkers in Urine, Plasma, and Serum)

Urine, plasma and serum samples will be obtained at predetermined times as indicated in the Schedule of Events ([Appendix 1](#) [Parts B and C] and [Appendix 2](#) [Part D]). These samples

will be used to measure specific proteins, peptides, metabolites and/or mRNA transcripts that may be elevated in patients with inflammatory/fibrotic disease or act as PD markers that may change with inhibition of $\alpha_v\beta_6$. [REDACTED]

[REDACTED]
[REDACTED]
[REDACTED]
Details of sample collection, storage, and assay will be provided in the study manual.

A table of exploratory biomarkers of interest and evidence for their prognostic or pharmacodynamic value is presented below.

Category	Biomarker	Evidence of Prognostic or Pharmacodynamic Value

[REDACTED]
	
[REDACTED]
	
[REDACTED]

	
[REDACTED]
	
[REDACTED]

	
[REDACTED]
	
[REDACTED]

	
[REDACTED]
	
[REDACTED]

[REDACTED]
	
[REDACTED]
	
[REDACTED]

	
[REDACTED]
	
[REDACTED]

	
[REDACTED]
	
[REDACTED]

	
[REDACTED]
	
[REDACTED]

	
[REDACTED]
	
[REDACTED]

[REDACTED]
	
[REDACTED]
	
[REDACTED]

[REDACTED]
	
[REDACTED]
	
[REDACTED]

[REDACTED]
	
[REDACTED]
	
[REDACTED]

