3.3 Secondary Pharmacodynamic Endpoints

- Presence or actual concentration of biomarkers in urine, plasma, or serum samples.
- Levels of biomarkers markers as well as relative (and/or absolute) change in levels for each participant and the relationship between these markers.
- Relationships between PK and PD may be evaluated in an exploratory fashion and presented in graphical manner.

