6.12 Pharmacokinetic Analyses

6.12.1 Concentration-Time Data

In study Parts B and C, plasma samples will be taken [REDACTED] relative to PLN-74809 dosing on [REDACTED]. In study Part D, plasma samples will be taken [REDACTED] relative to PLN-74809 dosing on [REDACTED].

Concentration data will be obtained for PLN-74809 [REDACTED].

[REDACTED] PLN-74809 concentration [REDACTED] will be calculated as follows:

- [REDACTED]
- [REDACTED]

PLN-74809 concentration data ([REDACTED]) will be summarized by dose level and visit at each scheduled sample time (nominal time) using descriptive statistics: number of non-missing observations (n), arithmetic mean (mean), standard deviation (SD), median, minimum (min), maximum (max), and coefficient of variation (CV%). Scatter plots will also be provided showing mean (SD). Similarly, [REDACTED] will be

QM [REDACTED]	[REDACTED]
Confidentiality Statement	
This document is the property of [REDACTED] and may not be duplicated, copied, altered or removed from company without prior approval from [REDACTED] or in compliance with [REDACTED]	

Controlled Quality Management Document		
	Sponsor:	Pliant Therapeutics Inc.
	Protocol Number:	PLN-74809-IPF-202
STATISTICAL ANALYSIS PLAN. PHASE 2-3-4		

summarized. Concentrations that are below the limit of quantification (BLQ) will be set to zero for summary statistics. BLQ concentrations will be retained as BLQ in listings. The data will be reported to 3 significant figures.

Individual PLN-74809 [REDACTED] [REDACTED]), nintedanib, and pirfenidone concentration data will be provided in listings. Data may be pooled with data from other studies for population PK and reported outside of the clinical study report.

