6.13 Pharmacodynamic Analyses

Biomarker results obtained from urine, plasma or serum samples will be summarized using descriptive statistics by treatment group and visit for each parameter. Actual biomarker concentration at each visit, the change from baseline and percentage change from baseline will be presented. The result adjusted for dilution factor will be used in summaries and listings. Samples hemolyzed, received ambient or with a note indicating improper storage will be excluded from summaries and listed only. If a sample has been excluded, then the change from baseline for that sample will also not be calculated.

Actual biomarker concentrations will be presented as a line plot showing the mean (\pm SD) concentration at each visit by treatment group for each parameter.

For biomarkers with at least 2 post-baseline scheduled assessments, absolute change from baseline and percentage change from baseline will be presented as a line plot showing baseline (0) and the mean (\pm SD) concentration at each post-dose visit by treatment group for each parameter.

For biomarkers with only one post-dose scheduled assessment, absolute change from baseline and percentage change from baseline will be presented by box and whisker plot for each treatment group.

Change from baseline to each visit will also be analyzed for all biomarkers using an MMRM [REDACTED] [REDACTED] LS means (\pm SE) for each treatment group and estimate for treatment difference compared to placebo, with corresponding SE, 95% CI and p-value will be provided .

QMD [REDACTED]	[REDACTED]
Confidentiality Statement	
This document is the property of [REDACTED] and may not be duplicated, copied, altered or removed from company without prior approval from [REDACTED] or in compliance with [REDACTED].	

Controlled Quality Management Document		
	Sponsor:	Pliant Therapeutics Inc.
	Protocol Number:	PLN-74809-IPF-202
STATISTICAL ANALYSIS PLAN. PHASE 2-3-4		

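### On the readable text, biomarker results recorded as '< x' are analysed as x, which pulls the treatment difference towards zero for any marker that reaches an assay limit

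*SAP*

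**What the plan says.** SAP 6.2.15 is a general derived-data rule. It opens "In the case where a variable is recorded as" greater than, at least, less than or at most x, and it ends "a value of x will be taken for analysis purposes". It neither names biomarkers nor excludes them.

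SAP 3.3 defines the pharmacodynamic endpoint as "Presence or actual concentration of biomarkers in urine, plasma, or serum samples". SAP 6.13 then specifies the analysis: "Actual biomarker concentration at each visit, the change from baseline and percentage change from baseline will be presented", and "Change from baseline to each visit will also be analyzed for all biomarkers using an MMRM", with a difference from placebo, standard error, 95% CI and p-value. It also has data-handling rules of its own. Badly handled samples are left out of the summaries, and on dilution it says "The result adjusted for dilution factor will be used in summaries and listings". No rule for results below an assay limit is readable there.

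The only other readable below-limit rule is in SAP 6.12.1: "Concentrations that are below the limit of quantification (BLQ) will be set to zero for summary statistics". That section concerns PLN-74809 plasma concentrations.

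**The concern.** Scoring '< x' as x replaces each below-limit result by a value at or above the true one. Protocol 7.11 says the samples will be used to measure "proteins, peptides, metabolites and/or mRNA transcripts that may be elevated in patients with inflammatory/fibrotic disease", among other markers that may change with target inhibition. For a marker that is raised in disease, a fall is a plausible drug effect. A fall moves more active than placebo results under the limit, so the error does not cancel between groups.

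The study is dose-ranging, and Protocol 3.2 says its findings will inform dose selection for later IPF studies. If the dose with the largest true effect loses the largest share of it, the contrast between doses is compressed on the affected markers.

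**Working it through.** The plan states no figure on this point, so there is none to reproduce. The check has four steps.

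**1. Individual values.** With limit x, the rule replaces a result y by max(y, x).
- Marker falls from 1.5x to 0.5x: the true change is (0.5 - 1.5)/1.5 = -67%; the scored change is (1.0 - 1.5)/1.5 = -33%.
- Marker below x at both visits: the scored change is exactly 0, whatever the true change.

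**2. Size at a true 30% fall.** All of these inputs are assumptions, because the documents give none of them:
- baseline y0 = b·w0 and follow-up y1 = b·w1·(1 - 0.30)
- b lognormal with geometric SD (GSD) 1.5 or 2.0
- w0 and w1 lognormal with log-SD 0.2
- limit L set at a quantile of y0
- scored values max(y0, L) and max(y1, L).

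On placebo, baseline and follow-up have the same distribution, so mean change is zero under either scoring. The retained share of mean change on active is therefore also the retained share of the active-placebo difference.

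The true mean percent change is 0.70 × exp(0.2²) - 1 = 0.70 × 1.041 - 1 = -27.1%.

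| Baseline values below limit | Share of mean change retained, GSD 1.5 / 2.0 | Understated by | Scored mean percent change, GSD 1.5 / 2.0 (true -27.1%) |
|---|---|---|---|
| 2% | 0.98 / 0.99 | about 1-2% | -26% / -26% |
| 10% | 0.91 / 0.96 | 4-9% | -22.4% / -23.3% |
| 20% | 0.81 / 0.91 | 9-19% | -18.7% / -20.0% |
| 40% | 0.63 / 0.77 | 23-37% | -12.8% / -14.0% |

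Repeat simulations agree to rounding; the 0.81 comes out as 0.82 in some.

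A second set of assumptions gives the same direction: log-SD 0.5 or 1.0, baseline/follow-up correlation 0.8, true falls of 30% or 50%. The shares of the active-placebo difference retained were:

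| Baseline values below limit | Absolute change | Percent change |
|---|---|---|
| 2% | 0.96-1.00 | 0.92-0.98 |
| 10% | 0.86-0.98 | 0.76-0.88 |
| 30% | 0.65-0.91 | 0.50-0.67 |
| 50% | 0.46-0.80 | 0.31-0.46 |

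No setting was biased away from zero. For a marker rising by 50%, with the same lower limit, the retained share of percent change was 0.56-0.99.

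**3. Dose-response.** With GSD 1.5 and 20% of baseline values below the limit, the retained shares for true falls of 10%, 30% and 50% are 0.88, 0.81 and 0.71 (percent change: 0.78, 0.70 and 0.59). The true ratio of the largest to the smallest effect is 50/10 = 5.0. The scored ratio is (50 × 0.71)/(10 × 0.88) = 35.5/8.8 = 4.0. The order of the doses is kept and the contrast shrinks.

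**4. Behaviour under the null.** The plan implies 28 × 3/4 = 21 participants in each of Parts B and D on active, 56 × 3/8 = 21 on each Part C dose, and 7 + 14 + 7 = 28 on placebo. With 21 against 28, GSD 1.75 and 10%, 40% or 60% of baseline values below the limit, a two-sided 5% t-test on scored change rejected in 4.7%, 4.8% and 4.5% of simulated trials.

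**The case against.** **It is not shown that the rule reaches any biomarker.** It applies to values recorded with an inequality sign. Neither document says whether the biomarker laboratory reports low results as '< x', as BLQ or as an extrapolated number. The marker table in Protocol 7.11 is redacted. A reader might infer from the wording of the endpoint in SAP 3.3 that undetectable results are expected. That wording allows for them but does not say they will occur. This objection stands, and it is why the point is conditional.

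**An exception may be redacted.** The model specification in SAP 6.13 is blacked out, and so are SAP 6.2.16 to 6.2.19. The amendment table and SAP 6.15.2 identify 6.2.17 as electrocardiogram abnormalities and 6.2.19 as liver abnormalities; the other two are unknown. This also stands.

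**Standard errors.** A reader might infer that replacing unknown low values by a constant gives falsely small standard errors and spurious significance. The check does not support this. The same transformation applies to every group, and the null rejection rate stays near 5%. The smaller SD belongs to the smaller scored change. In the second set of assumptions with 10% below the limit, the standardised effect for a falling marker also drops, to 0.71-0.93 of its true value.

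**Importance.** Protocol 12.1 says that no hypotheses are tested. SAP 2.3 lists biomarker change as an exploratory objective, although SAP 3.3 labels the endpoints secondary. No readable decision rule uses a biomarker p-value. This limits the weight of the point but does not remove it.

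**Every substitution is a convention.** That is partly right. For a falling marker, the shares of the true difference in absolute change obtained with two alternatives were:
- x/2: 1.00-1.07, 0.98-1.06 and 0.83-0.95 with 10%, 30% and 50% of baseline values below the limit
- zero: 1.03-1.27, 1.07-1.37 and 1.06-1.33, which overstates the effect.

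Neither is generally unbiased. This argues for a censored analysis over another fixed value.

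**Conclusion.** The point holds in conditional form. SAP 6.2.15 is a stated rule, not merely a missing detail, and nothing readable exempts biomarkers from it. For any marker with results recorded as '< x' it attenuates the active-placebo difference, and the loss grows with the true fall. Results recorded as '> x' cap a rise in the same way. The harm is attenuation and lost sensitivity.

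The size cannot be fixed from the documents. It runs from nothing for a marker that never reaches a limit, through 4-9% of mean change with 10% of baseline values below the limit, to 23-37% with 40%. Those figures assume lognormal markers, a 30% true fall and the stated variances. The direction assumes that treatment shifts the marker one way.

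A reader might go further and conclude that the trial's pharmacodynamic results are biased as a matter of fact. The documents do not support that without the marker list, the reporting format and the below-limit rates. The primary safety endpoint is unaffected.

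**What to change.** If a redacted passage already deals with below-limit biomarker results, the sponsor need only confirm it. Otherwise, in SAP 6.2.15 and 6.13:

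- State that biomarker analyses do not rely on the substitution of x alone.
- Tabulate the number and percent of results beyond the assay limit, by treatment group and visit, for each marker. This shows at once whether the issue is material.
- For markers with a non-trivial share beyond the limit, report a censored-likelihood analysis of the treatment difference beside the substitution result. The sponsor should set the threshold in advance; 10% is an example and has no basis in the documents. With about 21 participants per dose, the model may fail for heavily censored markers. Where it does not converge, report substitution at x and at x/2.

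One tempting addition should be avoided: leaving out a participant's percent change when both values are below the limit. That excludes participants on a post-randomisation outcome and does so unequally. With GSD 1.5, a 30% fall and 40% of baseline values below the limit, it would drop 39% of active against 30% of placebo participants.

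The cost is SAP wording, some programming and a distributional assumption in the censored model. No new samples or participants are needed. SAP section 6 allows additional analyses in the study report with documented justification, and the SAP already carries an addendum issued after final database lock, so there is a route for the change.

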6.2.20 Determination of FVC outliers

[REDACTED]
[REDACTED]
[REDACTED]
[REDACTED]
[REDACTED]

[REDACTED]

[REDACTED]

[REDACTED]

[REDACTED]

[REDACTED]

[REDACTED]

[REDACTED]

[REDACTED]

[REDACTED]

[REDACTED]

[REDACTED]

[REDACTED]

[REDACTED]

[REDACTED]

Confidentiality Statement	
This document is the property of [REDACTED] and may not be duplicated, copied, altered or removed from company without prior approval from [REDACTED] or in compliance with [REDACTED].	

[REDACTED]

Controlled Quality Management Document		
	Sponsor:	Pliant Therapeutics Inc.
	Protocol Number:	PLN-74809-IPF-202
STATISTICAL ANALYSIS PLAN. PHASE 2-3-4		

6.3 Conventions

6.3.1 Medical Coding

Adverse events and medical history will be coded using the Medical Dictionary of Regulated Activities (MedDRA) Version 24.1 (or higher). Conditions will be assigned to a System organ class (SOC) and preferred term (PT) based on the Investigator-reported verbatim term.

Any medications taken (other than study drug) will be coded using the World Health Organization Drug Dictionary (██████████) September 2021 Version (or higher). Medications (both prior and concomitant) will be assigned to an Anatomical Therapeutic Chemical (ATC) Level 4 drug classification and Preferred Name based on the medication name reported on the eCRF.

6.3.2 Data Handling

All clinical data programming will be performed using ██████████ ██████████ ██████████ and based on Clinical Data Interchange Standards Consortium (CDISC) data standards.

Study Data Tabulation Model (SDTM) programming will follow SDTM version 1.7 together with SDTM implementation guide 3.3. Analytical Data Model (ADaM) programming will follow ADaM implementation guide 1.1. Specifications for SDTM and ADaM datasets are described in a separate document.

6.3.3 Validation Methods

All programming of datasets and outputs will be validated by fully independent double programming of values and manual review of format compared to the SAP and agreed shell template. Figures will be validated by manual review of format and visual inspection of graphical display compared to tabulated data. All tables, figures and listings will be reviewed by a statistician prior to each milestone delivery.

6.3.4 Summary Statistics

Continuous variables will be summarized by the number of non-missing observations, mean, median, standard deviation, and minimum and maximum.

Confidentiality Statement	
This document is the property of ██████████ and may not be duplicated, copied, altered or removed from company without prior approval from ██████████ or in compliance with ██████████.	

Controlled Quality Management Document		
	Sponsor:	Pliant Therapeutics Inc.
	Protocol Number:	PLN-74809-IPF-202
STATISTICAL ANALYSIS PLAN. PHASE 2-3-4		

Categorical variables will be summarized by presenting the frequency and percent. Percentages will be based on the number of non-missing observations or the participant population unless otherwise specified. For each variable, all categories will be shown. Zero frequencies (but not the percent) within a category will be presented.

Incidences of adverse events, medical history and concomitant medications will be reported at the participant level. Participants can only be counted once within each PT and SOC under the highest severity and most related. Percentages will be calculated using the number of participants in the treatment group for the Safety Population.

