6.3.6 Data Displays

All clinical data tabulations, figures and listings will be generated as individual Rich Text Format (.rtf) files using [REDACTED]¹. Data summaries and graphical analyses will be reported within Section 14 of the CSR and individual participant data listings within Appendix 16.2 of the CSR.

Participant disposition, baseline characteristics, demographic, compliance, concomitant medication, and adverse event data will be presented by treatment group and overall. Other safety data will be presented by treatment group only.

Please note: Data from study Part A will be listed only.

Treatment group labels will be displayed as follows:

PLN-74809	PLN-74809	PLN-74809	PLN-74809	All	
(40 mg)	(80 mg)	(160 mg)	(320 mg)	PLN-74809	Placebo
(N=XX)	(N=XX)	(N=XX)	(N=XX)	(N=XX)	(N=XX)

QMD [REDACTED]	[REDACTED]
Confidentiality Statement	
This document is the property of [REDACTED] and may not be duplicated, copied, altered or removed from company without prior approval from [REDACTED] or in compliance with [REDACTED].	

[REDACTED]

Controlled Quality Management Document		
	Sponsor:	Pliant Therapeutics Inc.
	Protocol Number:	PLN-74809-IPF-202
STATISTICAL ANALYSIS PLAN. PHASE 2-3-4		

Listings will be sorted in the following order, study part (Parts B/C/D/A), treatment group, participant number, parameter, and visit unless otherwise stated. All data will be listed, participants who were not randomized will be displayed after the randomized treatment groups.

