6.6 Baseline Comparability

Comparability of treatment groups with respect to participant demographics and baseline characteristics will be assessed in a descriptive manner, but no formal statistical testing will be performed.

Baseline summaries will be presented by treatment group and overall, for the following variables based on the Safety Population:

Demographic Data

- Age at Informed Consent (years)
- Sex
- Ethnicity

Confidentiality Statement	
This document is the property of [REDACTED] and may not be duplicated, copied, altered or removed from company without prior approval from [REDACTED] or in compliance with [REDACTED].	

[REDACTED]

Controlled Quality Management Document		
	Sponsor:	Pliant Therapeutics Inc.
	Protocol Number:	PLN-74809-IPF-202
STATISTICAL ANALYSIS PLAN. PHASE 2-3-4		

- Race, where more than one race is selected the participant will be presented under the ‘Multiple races’ category in the summary but each selected race will be identified in the listing.

Baseline Characteristics

- Weight at Screening (kg)
- Height at Screening (cm)
- BMI at Screening (kg/m²)
- Fertility Status (Childbearing Potential, Postmenopausal, Surgically Sterile)
- Participant taking nintedanib or pirfenidone at Screening

Clinical Characteristics

- Pulmonary Function at Screening
- Pulmonary Function at Baseline
- DLCO Lung Function Assessment at Screening (if repeated, the last non-missing value before first dose will be taken)
- GAP Index Score and Staging
- Duration Since Diagnosis at Screening (first date reported for Idiopathic Pulmonary Fibrosis, Pulmonary Fibrosis or Interstitial Lung Disease)
- Duration of Standard of Care at Randomization (defined as the number of months from start date of nintedanib or pirfenidone to date of randomization)

Additional summaries will be completed for Part D only participants as well as placebo participants by study part.

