6.9 Exposure to Study Drug

Duration of exposure (in days) will be summarized by treatment group for the Safety Population. All exposure data, including changes in dosing recorded, will be listed.

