6.15.1 Adverse Events

AE analyses will be presented by the treatment received for the Safety Population. Tabulations will be presented overall and by SoC (Yes, No).

AEs will be collected from the time of informed consent through completion of the participant's last study visit.

A treatment emergent adverse event (TEAE) is defined as:

- Any AE that has an onset on or after the first dose of study drug through completion of the last study visit.
- Any pre-existing AE that has worsened in severity on or after the first dose of study drug through completion of the last study visit.

AEs occurring prior to first dose are considered non-treatment emergent and will be listed only.

The Investigator will determine the relationship of the AE to treatment (Related, Not Related). If an AE has missing relationship it is assumed to be related to the study drug for analysis purposes.

Severity of the AE will be graded using the Common Terminology Criteria for Adverse Events (CTCAE) grading system (Version 5.0): Grade 1 (Mild), Grade 2 (Moderate), Grade 3 (Severe), Grade 4 (Life-Threatening), Grade 5 (Fatal). Grade 3 (Severe) will be assumed for an AE with missing grade.

An overall summary of AEs (incidence and number of events) will be presented by treatment group and overall, for the following:

- Any AE
- TEAE
- TEAE Related to Study Drug

QMD [REDACTED]	[REDACTED]
Confidentiality Statement	
This document is the property of [REDACTED] and may not be duplicated, copied, altered or removed from company without prior approval from [REDACTED] or in compliance with [REDACTED].	

[REDACTED]

Controlled Quality Management Document		
	Sponsor:	Pliant Therapeutics Inc.
	Protocol Number:	PLN-74809-IPF-202
STATISTICAL ANALYSIS PLAN. PHASE 2-3-4		

- TEAE Related to a Study Procedure
- Serious TEAE
- Serious TEAE Related to Study Drug
- TEAE of CTCAE Grade 3 or Higher
- TEAE of CTCAE Grade 3 or Higher Related to Study Drug
- TEAE Leading to Interruption of Study Drug
- TEAE Leading to Withdrawal of Study Drug
- TEAE Leading to Early Termination from Study
- TEAE Leading to Death

Summaries of TEAEs (incidence and number of events) will be presented by SOC and PT, by treatment group and overall, for the following:

- TEAE
- TEAE Related to Study Drug
- Serious TEAE
- Serious TEAE Related to Study Drug
- TEAE Related to a Study Procedure
- TEAE of CTCAE Grade 3 or Higher
- TEAE of CTCAE Grade 3 or Higher Related to Study Drug
- TEAE Leading to Interruption of Study Drug

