7 INTERIM ANALYSIS

Interim analyses will be conducted at the following milestones:

- Upon completion of Parts B and C (following full enrollment and 12-week treatment duration with 40, 80, or 160 mg PLN-74809).
- Upon completion of 12-week treatment duration with 320 mg PLN-74809 in Part D.

A database freeze will occur upon completion of study Part C by the last participant. All data for study part A, B and C will be 100% cleaned and signed off by the investigators. After database freeze, participants will be unblinded and these data will be used for the statistical analysis and reporting of Parts A, B and C.

Blinding measures for interim analyses performed on data up to Week 12 for all participants in Part D will be described in a separate blinding plan.

Interim data from Part D will include all assessments up to the Week 12 assessments, [REDACTED] Adverse events or concomitant medications started/initiated post Day [REDACTED] will not be summarized in the in the interim analysis and will be presented in the final analysis. Participants who discontinue treatment or the study post the Week 12 assessment date up to Day [REDACTED] will be summarized as on treatment/on study for the purposes of the interim analyses.

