9 CHANGES TO PLANNED PROTOCOL ANALYSIS

1. Adverse event summaries and efficacy assessments will be presented overall and [REDACTED]
2. Change from Baseline at Week 12 in efficacy assessments will also be presented by [REDACTED]

QMD [REDACTED]	
Confidentiality Statement	
This document is the property of [REDACTED] and may not be duplicated, copied, altered or removed from company without prior approval from [REDACTED] or in compliance with [REDACTED].	

Controlled Quality Management Document		
	Sponsor:	Pliant Therapeutics Inc.
	Protocol Number:	PLN-74809-IPF-202
STATISTICAL ANALYSIS PLAN. PHASE 2-3-4		

3. [REDACTED]
4. A mixed model for repeated measures [REDACTED].
5. Definition of Efficacy Per Protocol Population was revised from:
[REDACTED]
6. Removed CTCAE grading summaries for laboratory test parameters.
[REDACTED]
8. Added additional pooled placebo groups for comparison purposes.

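### Final AE tables: crude percentages set 320 mg (about 26–50 weeks at risk) beside a pooled placebo column that is three-quarters at about 14 weeks

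*SAP*

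**What the plan says.** SAP 6.3.4 counts each participant once per preferred term and system organ class. It then fixes the denominator: "Percentages will be calculated using the number of participants in the treatment group for the Safety Population".

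SAP 6.3.6 says that "adverse event data will be presented by treatment group and overall". Its column layout is 40, 80, 160 and 320 mg, All PLN-74809, and a single Placebo column.

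SAP 6.15.1 defines a TEAE to include "Any AE that has an onset on or after the first dose of study drug through completion of the last study visit", so all of the Part D extension and the two-week follow-up count. The only readable split of the AE tables is by standard-of-care use.

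Four other provisions bear on the point:

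- SAP 6.9: "Duration of exposure (in days) will be summarized by treatment group for the Safety Population". This is a separate table and enters no AE denominator.
- SAP 6.6: "Additional summaries will be completed for Part D only participants as well as placebo participants by study part". This sits under Baseline Comparability.
- SAP 7 cuts the Part D interim at about Week 12. AEs starting after the cut-off day "will not be summarized in the in the interim analysis and will be presented in the final analysis".
- SAP 9, item 1: "Adverse event summaries and efficacy assessments will be presented overall and". The rest of that sentence is blacked out.

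**The concern.** Dose and follow-up time are tied together by design. The 320 mg dose exists only in Part D, and 40, 80 and 160 mg only in Parts B and C. The placebo column mixes the two, mostly at the shorter follow-up. A crude percentage over unequal time at risk rises with time, so the 320 mg column has a head start over placebo for any event that keeps occurring after about Week 14, and the lower doses have a handicap.

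The primary endpoint is the nature and proportion of AEs between PLN-74809 and placebo groups (SAP 3.1). Protocol 12.5.1 asks for SAEs and AE withdrawals by treatment and dose, and Protocol 3.2 says that the findings will inform dose selection. Lower doses below placebo and the top dose above it would look like a dose-related safety signal, and the layout alone can produce that pattern.

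**Working it through.** **Plan's own figures.** From Protocol 6.4 and SAP 5:

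- Active: 28×3/4 + 56×3/8 + 56×3/8 + 28×3/4 = 21 + 21 + 21 + 21 = 84.
- Placebo: 28/4 + 56×2/8 + 28/4 = 7 + 14 + 7 = 28.

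These match the approximate totals of 84 and 28 in Protocol 3.1. That section also gives 29 randomized in Part B. With 29, the Part D share of placebo is 24–25%, which changes nothing material.

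**Follow-up from first dose** (Protocol 3.3).

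- Parts B and C: 12 + 2 = 14 weeks.
- Part D: 24 + 2 = 26 weeks up to 48 + 2 = 50 weeks.
- The Part D schematic note in Protocol 3.1 puts the last participant's end of treatment at Week 26, which would make the minimum 28. The two passages need reconciling.

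**Mean placebo follow-up.** With Part D at 26 weeks it is 0.75×14 + 0.25×26 = 17, so 320 mg has 1.53 times as long. With Part D at 50 weeks it is 23, a ratio of 2.17.

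**Direction, with no assumed rate.** Let F(t) be the cumulative incidence with no drug effect, the same in every part, and T the Part D follow-up.

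- 320 mg column: F(T).
- Placebo column: 0.75·F(14) + 0.25·F(T).
- 320 mg minus placebo: 0.75·[F(T) − F(14)]. This is never negative, and is zero only if nothing starts after Week 14.
- 40–160 mg minus placebo: −0.25·[F(T) − F(14)].
- All PLN-74809: (63·F(14) + 21·F(T))/84, which equals placebo.

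**Size, with assumed rates.** Assume a 14-week risk p of 5%, 10% or 30%, and F(t) = 1 − exp{ln(1−p)·(t/14)^k}. Here k = 1 is a constant hazard and k = 0.5 is early clustering. For 26–50 weeks, F is averaged over an even spread of T, which is a further assumption.

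Worked case, p = 10%, k = 1, T = 26: F(26) = 1 − 0.9^(26/14) = 17.8%. Placebo = 0.75×10 + 0.25×17.8 = 11.9%. Excess = 5.8 points from unrounded values.

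The last column is the chance of an observed excess of at least 10 points, exact from binomials with 21 on 320 mg and 21 + 7 on placebo. The 10-point mark is illustrative and not taken from the documents.

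| Onset pattern, Part D follow-up | Expected excess in points (p = 5 / 10 / 30%) | Chance of excess ≥ 10 points |
|---|---|---|
| Constant, 26–50 weeks | 6.0 / 11.1 / 23.6 | 32 / 52 / 83% |
| Constant, 26 weeks | 3.1 / 5.8 / 13.8 | 18 / 33 / 61% |
| Early clustering, 26–50 weeks | 2.3 / 4.4 / 10.7 | 15 / 28 / 52% |
| Early clustering, 26 weeks | 1.3 / 2.5 / 6.4 | 10 / 21 / 39% |
| Equal risk in both columns | 0 | 6 / 13 / 22% |

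With a 28-week minimum instead of 26, the excess is 3.6 / 6.8 / 15.8 (constant) and 1.5 / 2.9 / 7.2 (early clustering).

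With 10% dropout per 14 weeks, the first row becomes 4.9 / 9.1 / 19.5 points (chance 27 / 45 / 75%). The fourth becomes 1.1 / 2.2 / 5.5 points (chance 9 / 20 / 37%).

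Without dropout, the 40–160 mg columns are expected below placebo by 0.4–2.0, 0.8–3.7 and 2.1–7.9 points for the three risks.

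**The case against.** The strongest objection is that the absence cannot be verified. The whole list of tables in SAP 11 is blacked out, as are a line after the TEAE summaries in 6.15.1 and the end of SAP 9 item 1, which is about how AE summaries are split. Tables by part or adjusted for exposure may be specified there. This stands, and it limits the claim to the readable text.

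Second, the reader is not helpless. Exposure is tabulated by group, listings are sorted by study part, and the Part D interim is cut at about Week 12. These reduce the harm, but none of them enters the final AE tables. SAP 7 does not say that the interim shows every dose, and the cut-off day is redacted. The separate Part D comparison in SAP 6.11.1 is for FVC only.

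Third, the endpoint is descriptive, no hypothesis is tested, and All PLN-74809 versus placebo is balanced. That is correct. What remains is the per-dose reading of later-onset AEs, which a dose-ranging study invites.

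Fourth, the size is uncertain. Fifty weeks is the documents' maximum, dropout and early clustering shrink the gap, and one participant in 21 is already 4.8 points. This also stands. The direction does not depend on it, but a single rare AE can still fall the other way by chance.

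**Conclusion.** The concern holds for the readable plan. In the final per-dose AE tables, 320 mg versus placebo is not like-for-like for AEs that can start after about Week 14, and the expected bias is against 320 mg and in favor of 40–160 mg. Across the cases run, the spurious 320 mg excess is 1.1 to 23.6 points.

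The direction rests on the planned allocation and follow-up, and on equal background risk across parts. The size rests on assumed AE rates, onset patterns and dropout. Event counts in the same tables share the problem. The pooled active-versus-placebo comparison is sound, AEs confined to the first 14 weeks are unaffected, and no data are lost. This should be fixed. Confidence is medium, because the relevant table list is redacted.

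**What to change.** In SAP 6.15.1, for the final analysis:

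1. Add an all-dose AE table restricted to onset from first dose through Week 12 in every part, with the same cut as the Part D interim. Both columns then estimate F(12), and the bias from follow-up time is zero. This table should come first.
2. Show exposure-adjusted incidence (participants with the event per participant-time at risk) beside the crude percentages. Under a constant hazard it is equal in both columns. For a 14-week risk of 10% it is −ln(0.9)/14 × 52.18 × 100 = 39.3 per 100 participant-years. It corrects only approximately if AEs cluster early.
3. Tabulate full Part D follow-up as 320 mg versus Part D placebo, noting that it rests on about 7 placebo participants.

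If redacted tables already do this, a cross-reference in 6.15.1 is enough.

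The cost is SAP wording and extra tables on data already collected. The amendment log includes an addendum after final database lock, so these may have to be labeled as post-lock additions. SAP 6 allows additional tables in the CSR with documented justification.
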